#### Spettrophotometry examination and TEWL examination

Objective in vivo measurements of skin erythema and pigmentation based on reflectance spectrometry (RS) will be performed. Skin reflectance measurements will be acquired in vivo by a spectrophotometric imaging system (SkinColorCatch, by Delfin Technologies Ltd. – Finland). At the clinical site, the Medical Physics Unit has a long tradition with spectrophotometric analysis, having developed a tool for automated melanoma detection and for the description of the blood and melanin content of pigmented skin lesions.

Measurements will be performed before RT start and then once a week at each visit before RT session and on clean skin. Instrumental RS measurements will be performed at three different fixed regions within the area treated with RT, in any case only on flat skin regions and in absence of hair or nevus. A control measurement will be done also in a specific contralateral area.

The trans-epidermal water loss (TEWL) exam will be done at the same time-points as for the spettrophotometry exam, before RT sessions. The exam will be conducted with VapoMeter instrument (Delfin Technologies Ltd. – Finland).

Measurements will be performed before RT start and then once a week at each visit, before RT session and on clean skin. Instrumental TEWL measurements will be performed at five different fixed regions within the area treated with RT, in any case only on flat skin regions and in absence of hair or nevus. A control measurement will be done also in a specific contralateral area.

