### 11.4.2 Secondary Efficacy Endpoints

The median time to G2 radiation dermatitis development will be analyzed using Kaplan-Meier method.

Comparisons between treatment groups will be performed using log-rank test.

```
proc lifetest;
time time_to_G2 * G2_yn(0);
strata treatment / test=( logrank );
test treatment;
run;
```

The proportion of patients without G2 radiation dermatitis at week 6 for both cancer sites, at week 7 for head & neck cancer and 2 weeks after the last radiation for both cancer sites will be assessed and compared between treatment groups using chi-square test. Logistic regression will be used to obtain ORs, with 95% CIs, and to eventually adjust for covariates. The same method used for primary objective will be applied.

The changes in skin erythema and pigmentation will be graphically described reporting the ITA (individual Typological Angle) degrees throughout the study. The ITA of the area treated with RT will be obtained averaging the ITA measured at the three different fixed regions, adjusted for the control measurement done in a specific contralateral area. Changes between visit 2, before the first RT session, and the end of RT and between the end of RT and the end of treatment will be analyzed and compared between treatment groups using ANCOVA, to adjust the estimates for baseline values.

The following SAS code will be used for ANCOVA analysis:

```
proc glm;
  class treatment;
  model avg_ITA = treatment avg_ITA_baseline;
  run;
```

where avg\_ITA at each timepoint and avg\_ITA\_baseline have been obtained as follows:

```
ITA_diff1 = ita_rt1 - ita_controlateral;
ITA_diff2 = ita_rt2 - ita_controlateral;
ITA_diff3 = ita_rt3 - ita_controlateral;
avg_ITA#= mean(ITA_diff1, ITA_diff2, ITA_diff3, ITA_diff4, ITA_diff5);
```

The changes in trans-epidermal water loss (TEWL) will be graphically described reporting the Evaporation rate value (ERV, measured in g/m^2h) throughout the study. The ERV of the area treated with RT will be obtained averaging the ERV measured at the five different fixed regions, adjusted for the control measurement done in a specific contralateral area. Changes between visit 2, before the first RT session, and the end of RT and between the end of RT and the end of treatment will be analyzed and compared between treatment groups using ANCOVA, to adjust the estimates for baseline values.

The following SAS code will be used for ANCOVA analysis:

```
proc glm;
  class treatment;

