  model avg_TEWL = treatment avg_TEWL_baseline;
  run;
```

where avg\_TEWL and avg\_TEWL\_baseline have been obtained as follows:

```
TEWL_diff1 = tewl_rt1 - tewl_ct;
TEWL_diff2 = tewl_rt2 - tewl_ct;
```

```

TEWL_diff3 = tewl_rt3 - tewl_ct;
TEWL_diff4 = tewl_rt4 - tewl_ct;
TEWL_diff5 = tewl_rt5 - tewl_ct;
avg_TEWL #= mean(TEWL_diff1,TEWL_diff2,TEWL_diff3,TEWL_diff4,TEWL_diff5);

```

The mean and worst score of Skindex-16 questionnaire will be compared between treatment groups using ANCOVA, to adjust the estimates for baseline values.

The following SAS code will be used for ANCOVA analysis:

```

proc glm data = DB;
class treatment;
model skindex_score = treatment skindex_score_b1 ;
run;

```

Both the number of daily product applications reported on the patient's diary and the amount of used product, estimated through the difference in tubes weight between delivery to patient and return, will be used to assess the compliance to experimental treatment. The consistency between the two assessments will be checked through linear regression.

The patients' global satisfaction with treatment, assessed by Likert scale, will be compared between treatment groups using Kruskal-Wallis test.

```

proc npar1way;
class TREATMENT;
var satisfaction;
run;

```

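### The SAP's ANCOVA code for ITA and TEWL does not compute the stated change from end of RT to end of treatment, and its baseline variable is undefined

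*SAP*

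**What the plan says.** For ITA, SAP 11.4.2 names the quantities to be compared: "Changes between visit 2, before the first RT session, and the end of RT and between the end of RT and the end of treatment". They are to be "compared between treatment groups using ANCOVA, to adjust the estimates for baseline values". The TEWL paragraph, the summary table in SAP 11.5 and Protocol 7.3.5.2 say the same, and the planned tables in SAP 14.2 are titled as changes.

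The SAP then gives the code that will be used: "model avg_ITA = treatment avg_ITA_baseline" for ITA and "model avg_TEWL = treatment avg_TEWL_baseline" for TEWL. The outcome is a value at one timepoint. The only subtraction in its derivation removes the contralateral control site, as in "ITA_diff1 = ita_rt1 - ita_controlateral"; no earlier visit is subtracted. Each model has a single baseline covariate.

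SAP 9.1.1, headed as the section on baseline values, lists summary statistics and names no visit. The instrumental readings start before radiotherapy ("Measurements will be performed before RT start and then once a week at each visit before RT session and on clean skin"), and the flow charts in Protocol Appendix 2 show them from visit 2, not at screening.

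**The concern.** The text describes two changes with different starting points; the code has one form, a level on a baseline. If that baseline is the visit-2 value, the end-of-RT value enters the second-interval model neither as part of the outcome nor as a covariate. The model then cannot separate what happened in the two weeks after RT from what had already happened during RT.

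That matters because the second interval is where post-RT recovery is assessed, in a separate two-week treatment phase, for a product described as reducing TEWL and promoting healing. A difference built up during RT and merely maintained could be presented as better recovery. A difference that disappears after RT could be presented as no difference in change.

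**Working it through.** **Inputs.** Analyses are run separately by cancer site (SAP 9.1), with 18 evaluable and 20 enrolled per arm (SAP 7). The significance level is 0.05 (Protocol 7.3). The documents give no SD, correlation or expected effect for ITA or TEWL, so those below are assumptions.

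**The plan's own figure.** The only design calculation is for the primary endpoint, 38.2% against 82.9%. The mean proportion is 0.6055.

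n = [1.960 × √(2 × 0.6055 × 0.3945) + 0.842 × √(0.382 × 0.618 + 0.829 × 0.171)]² / 0.447² = (1.355 + 0.517)² / 0.1998 = 17.5, so 18. Then 18 / 0.9 = 20. It reproduces and is used here only for the arm size.

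**Notation.** Y0, Y1 and Y2 are the values at visit 2, end of RT and end of treatment; T is treatment.

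**First interval.** If Y1 − Y0 = a + bT + cY0, then Y1 = a + bT + (c + 1)Y0. The treatment coefficient b is the same, so with a visit-2 baseline the printed code is adequate.

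**Second interval.** Least squares is linear in the outcome. With the same patients and the same covariates (T, Y0):

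coefficient for Y2 = coefficient for Y1 + coefficient for (Y2 − Y1).

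The coded result is therefore the end-of-RT difference plus the recovery difference. The identity is exact in complete data; simulation agreed to rounding error.

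**Size.** Assumptions: SD 1 at each visit; 18 or 20 per arm; correlation of visit 2 with both later visits 0, 0.3 or 0.5; correlation of end of RT with end of treatment 0.5, 0.7 or 0.9; no true recovery difference; 40,000 simulated trials per setting. With only 2,000 trials per setting the limits move by a point or two.

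| End-of-RT difference | Coded model: mean estimate | Coded model: significant | Change on T and Y0: mean estimate | Change on T and Y0: significant |
|---|---|---|---|---|
| 0 | 0.0 | about 5% | 0.0 | about 5% |
| 0.5 SD | 0.5 | 30-42% | 0.0 | about 5% |
| 0.8 SD | 0.8 | 63-80% | 0.0 | about 5% |
| 1.0 SD | 1.0 | 82-94% | 0.0 | about 5% |

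**Masking.** If a 0.8 SD difference at end of RT is fully lost afterwards, the coded coefficient is 0.8 − 0.8 = 0 and is significant in about 5% of trials. The change model estimates −0.8 and is significant in 63-100%.

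**If baseline meant the end-of-RT value.** A level model on (T, Y1) gives the same treatment coefficient as a change model on (T, Y1). With equal SDs, correlation ρ between Y1 and Y2, an end-of-RT difference d and no recovery difference, its expected value is d(1 − ρ). At d = 0.8 that is 0.8 × 0.5 = 0.40 for ρ = 0.5 and 0.8 × 0.1 = 0.08 for ρ = 0.9. It is significant in about 8-26% of trials.

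**The case against.** The strongest reply is that the visit-2 baseline is an inference. The SAP defines neither baseline variable, and its prose adjusts for baseline values in the plural after naming two intervals, which could mean the starting value of each. This stands as a limit on certainty, but it does not rescue the analysis. The code shows one baseline variable and no resetting, and the reset version conditions on a value measured after randomisation, so it still departs from a comparison of changes, as shown above.

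A second reply is that the code is schematic: a placeholder stands for several visits, and the prose and table titles all speak of changes. A programmer might therefore produce the right contrast. That is possible, but the SAP says this code will be used, and no between-visit change is derived anywhere in it.

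Third, the percentages are power to detect a genuine randomised difference in end-of-treatment level. They are errors only if the result is labelled a change. That is correct, and it is the label the SAP gives it. The planned plots of mean ITA and TEWL would let an attentive reader see parallel post-RT courses, but they would not correct the reported p-value.

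A reader might infer that the trial will report a false recovery effect. The documents do not support that: it needs an arm difference at end of RT that persists, and without one the coded test keeps its 5% level. Nor do they support reading any single percentage above as the expected error rate.

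**Conclusion.** Prose and code in SAP 11.4.2 disagree for the second interval, for both ITA and TEWL, and the baseline variable is undefined. With baseline as visit 2, the mismatch is a matter of algebra: the code estimates a difference in level, not the stated change. How often this would mislead depends on the assumed SD, correlations and end-of-RT difference, from no excess at a zero difference to a large majority of trials at 0.8 SD or more.

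The first-interval code is sound on the same reading. These endpoints are exploratory under SAP 9.3, and the primary endpoint and sample size are untouched. The point should be corrected, but it does not threaten the trial's main conclusion.

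**What to change.** - Define `avg_ITA_baseline` and `avg_TEWL_baseline` in SAP 9.1.1 as the visit-2 value taken before the first RT session.
- For the second interval, derive end-of-treatment minus end-of-RT for each measure, and model that change on treatment and the visit-2 baseline.
- Keep the existing level model for the first interval. If it is also reported at end of treatment, label it a difference in level, not a change.
- State with the result that the second change exists only for patients measured at both visits. Protocol 6.1 takes patients with G3 skin toxicity out of the study, so this group is selected after randomisation.

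The cost is one definition, one derived variable and one model line per measure, plus a sentence in the report. No new data are needed, because every reading is already scheduled.

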## 11.5 Summary of Efficacy Analyses

Endpoint	Analysis	Populations
Proportion of patients without G2 radiation dermatitis at week 5	The proportion of patients without G2 radiation dermatitis (radiation dermatitis < G2) at week 5 will be assessed and compared between treatment groups using chi-square test. Logistic regression will be performed to obtain Odds Ratio.	ITT
Median time to G2 radiation dermatitis development according to CTCAE	Median time to G2 radiation dermatitis will be analyzed using Kaplan-Meier method and compared between treatment groups using log-rank test.	ITT
Proportion of patients without G2 radiation dermatitis at week 6 for both cancer sites, at week 7 for head & neck cancer and 2 weeks after the last radiation for both cancer sites	The proportion of patients without G2 radiation dermatitis at week 6 for both cancer sites, at week 7 for head & neck cancer and 2 weeks after the last radiation for both cancer sites will be assessed and compared between treatment groups using chi-	ITT

weeks after the last radiation for both cancer sites.	square test. Logistic regression will be performed to obtain Odds Ratios	
Changes in skin erythema and pigmentation and trans-epidermal water loss (TEWL)	The changes in skin erythema and pigmentation and in trans-epidermal water loss (TEWL) will be graphically described throughout the study. Changes between before the first RT session and the end of RT and between the end of RT and the end of treatment will be analyzed and compared between treatment groups using ANCOVA, to adjust the estimates for baseline values.	ITT
Mean and worst score of Patient Reported Outcome (PRO) with Skindex-16 questionnaire performed weekly	Weekly mean and worst score of Skindex-16 questionnaire will be compared between treatment groups using ANCOVA, to adjust the estimates for baseline values.	ITT
Compliance to experimental treatment use	The compliance with the treatment will be assessed through a diary where the patient will record the daily product applications and through the difference in weight of tubes when delivered to patient and when returned by the patient. The consistency between the two assessments will be checked.	ITT
Patient global satisfaction with treatment as assessed by Likert scale	The patients' global satisfaction with treatment, assessed by Likert scale, will be compared between treatment groups using Kruskal-Wallis test.	ITT
Study product safety and tolerability	Adverse events, coded according to MedDRA, will be summarized by treatment arm in terms of the number of patients who experienced at least one AE, study product-related AE, serious AE, severe AE and the number of patients withdrawn due to AE will be summarized. For each SOC and preferred term, summaries will be made with respect to the proportion of patients having at least one occurrence of that event during the trial and the total number of events. The comparisons will be analyzed using chi-square test.	Safety

## 12. SAFETY EVALUATION

### 12.1 Extent of Exposure

### 12.2 Adverse Events

Adverse events will be coded according to MedDRA, version 21.1. AEs will be summarized by treatment arm in terms of the number of patients who experienced at least one AE, study product-related AE, serious AE, severe AE and the number of patients withdrawn due to AE will be summarized. The comparisons will be analyzed using chi-square test. For each SOC and preferred term, summaries will be made with respect to the proportion of patients having at least one occurrence of that event during the trial and the total number of events.

```
proc freq;
table treatment * cat_variable / CHISQ;
run;
```

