6.2 Investigational device and comparator

6.2.1 Xonrid®

The product under investigation is Xonrid®.

Name: Xonrid®

Formulation: Gel

Route of administration: Topical

Composition: the composition of Xonrid®, including ingredient function, as reported in the commercial available product, is reported in Table 4.

Xonrid® is a short term use, Class IIa Medical Device, a topical gel designed for RT-induced dermatitis. When applied to the target skin areas, Xonrid® forms a protective film, reduces the trans-epidermal water loss (TEWL) effect induced by external factors and increases moisturizing. The component responsible for the formation of this film is mainly Hyaluronic Acid, that also helps to achieve an optimal moisturizing effect. The other components responsible for the formation of this film are: polyacrylamide gluconolactone, and Xanthan gum. In particular, gluconolactone is a polyhydroxy acid, with a strong hygroscopic moisturizing power, as well as a glycerin effect. Moreover, the device includes sweet almond oil, known for its emollient, softening, nourishing and soothing properties, and is particularly effective in the treatment of dry, reddened and sensitive skin areas. It promotes the healing process by restoring the physiological hydration levels of the affected skin areas. It can be applied to the target areas including skin folds and creases, either presenting or not minor traumas or abrasions. On these bases, Xonrid® may represent a promising device for the prevention of radiation dermatitis.

Table 4: Xonrid® ingredients with relative function

Ingredient	Function
Glycerin (Glycerol)	Humectant
Gluconolactone, sodium benzoate, calcium gluconate	Preservative
Chamomilla recutita water	Masking agent
Xanthan gum	Rheology additive
C12-15 alkyl benzoate	Emollient
Ethylhexyl palmitate	Emollient
Disodium EDTA	Chelanting agent
Glyceryl stearate	Emollient
Prunus amygdalus dulcis oil	Emollient
Polyacrylamide, C13-14 isoparaffin, laureth-7	Viscosity increasing agent
Vitis vinifera extract, aqua, propylene glycol	Skin conditioning agent
Aqua	Solvent
Sodium hyaluronate	Skin conditioning agent
Propylene glycol, aqua, camelia sinensis extract	Skin conditioning agents
Propylene glycol, hydrolyzed RNA, hydrolyzed DNA	Skin conditioning agents

Raspberry ketone	Skin conditioning agent
Propylene glycol	Solvent
Tocopheryl acetate	Preservative/ Antioxidant agent

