6.2.1.1 Packaging and labelling

Xonrid® will be manufactured and provided for the study by Helsinn Healthcare SA, the Sponsor of this clinical investigation.

The study product shipment to the study site will be done only after the completion of all Ethics and Administrative procedures.

The product will be labeled as experimental treatment in accordance with Good Manufacturing Practice (GMP, Annex 13).

The primary package is a bottle containing 75 ml of gel. Subjects randomized to Xonrid® + SOC will receive a total of:

1. no. 12 bottles if head & neck cancer subjects
2. no. 4 bottles if breast cancer subjects.

The number of bottles assigned should be enough for the whole study duration (56 ± 2 days / 63 ± 2 days).

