14.2 Adverse Event Intensity/Causality

The Investigator, based on his direct observation or on subjects' report, will record the event according to the current version of CTCAE:

Grade 1 (Mild): asymptomatic or mild symptoms; clinical or diagnostic observations only;

intervention not indicated.

Grade 2 (Moderate): minimal, local or noninvasive intervention indicated; limiting age-appropriate instrumental daily life activities.

Grade 3 (Severe): medically significant but not immediately life-threatening; hospitalization or prolongation of hospitalization indicated; disabling; limiting self -care daily life activities.

Grade 4 (Life-threatening consequences): urgent intervention indicated.

Grade 5: Death related to AE.

The relationship of any AE to the product will be classified by the Investigator as follows:

Description	Definition
Certain	The AE is clearly related to the study product
Probable	The AE is likely related to the study product
Possible	The AE may be related to the study product
Unlikely	The AE is unlikely related to the study product
None	The AE is clearly not related to the study product
Unknown	Causality is not assessable, for one reason or another, e.g. because of insufficient evidence, conflicting data or poor documentation

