#### **4.2 Treatment Administration**

Subjects have been randomly allocated to one of the following groups:

- Group A: Xonrid® gel + standard of care (SOC) preemptive treatment according to MASCC guidelines;
- Group B: standard of care (SOC) preemptive treatment according to MASCC guidelines.

Both Groups started treatment on the first day of radiotherapy and went on until two weeks after the last radiotherapy session.

Group B subjects received an additional standard treatment (according to Investigator's opinion) at G2 skin toxicity development.

All subjects interrupted the treatment and the study in the case of G3 skin toxicity development. This subjects have been treated according to the Investigator's opinion.

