### 12.3 Other safety endpoints

Tolerability assessment will be based on the evaluation of site administration adverse events.

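### Study product-related adverse events are compared between arms although only Group A has the product, so the p-value only restates the Group A count

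*SAP*

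**What the plan says.** SAP 12.2 sets out several by-arm summaries. After the count of patients with any event, the text runs: "study product-related AE, serious AE, severe AE and the number of patients withdrawn due to AE will be summarized. The comparisons will be analyzed". The method named is chi-square. The code is generic, "table treatment * cat_variable / CHISQ", with no exact option and no exception for any category. Protocol 7.3.6, SAP 5.3 and the summary table in SAP 11.5 carry the same plan. There the chi-square sentence comes after the system organ class and preferred term summaries, but again nothing takes product-related AEs out.

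On who receives the product:

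- Protocol 6.2.1: "The product under investigation is Xonrid".
- Protocol 6.2.1.1, on supply: "Subjects randomized to Xonrid® + SOC will receive a total of" a stated number of bottles. No supply is described for the other arm.
- SAP 4.2: "Group B: standard of care (SOC) preemptive treatment according to MASCC guidelines".

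On attribution, Protocol 14.2 says: "The relationship of any AE to the product will be classified by the Investigator as follows". The top category reads "The AE is clearly related to the study product". Every other category except Unknown is also defined against the study product. SAP 4.3 confirms that the study is open label.

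**The concern.** A between-arm test is informative when the event could occur in either arm. An event related to Xonrid should not be recorded in a patient who never had Xonrid, and the investigator who assigns causality knows who had it. The null hypothesis of equal rates is then false as soon as one Group A event is called related. The test measures how often unmasked investigators attributed events to the gel. It does not measure whether the gel adds harm to standard care.

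The result can mislead in two directions. Enough attributed events give a significant safety difference whatever happens to AEs overall. A few give a non-significant p-value, which can be quoted as no difference in product-related events although no comparison was possible.

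**Working it through.** **Arm size.** The plan gives no figure for this comparison, so its sample size is reproduced only to fix the number per arm. SAP section 7 assumes 38.2% and 82.9%, two-sided 0.05 and 80% power. With pooled proportion 0.6055:

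n = [1.960·√(2·0.6055·0.3945) + 0.842·√(0.382·0.618 + 0.829·0.171)]² / (0.829 − 0.382)² = (1.355 + 0.517)² / 0.1998 ≈ 17.5, so 18 per group.

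This matches the plan. Allowing for 10% dropout, 18/0.9 = 20 per group. Allocation is 1:1 (Protocol 6.4.1) and SAP 9.1 has each cancer site analysed separately, so each test is about 20 against 20.

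**The test with Group B at zero.** For x of n patients against 0 of n, Pearson chi-square reduces to 2n·x/(2n − x), which is 40x/(40 − x) at n = 20. Group B contributes only its size. The expected count in each event cell is x/2. Fisher's exact test is shown for comparison.

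| Group A (of 20) | Group B (of 20) | Chi-square | Pearson p | Fisher p | Expected events per arm |
|---|---|---|---|---|---|
| 0 | 0 | not computable | – | – | 0 |
| 1 | 0 | 1.026 | 0.311 | 1.000 | 0.5 |
| 2 | 0 | 2.105 | 0.147 | 0.487 | 1.0 |
| 3 | 0 | 3.243 | 0.072 | 0.231 | 1.5 |
| 4 | 0 | 4.444 | 0.035 | 0.106 | 2.0 |
| 5 | 0 | 5.714 | 0.017 | 0.047 | 2.5 |

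Four patients are always enough for Pearson significance at 0.05. The factor 2n/(2n − x) exceeds 1, so at x = 4 the statistic exceeds 4, which is above the critical value of 3.841. If the sites were pooled at 40 per arm, x = 4 gives 320/76 = 4.211, p = 0.040. At these event counts the chi-square approximation is also poor: 4 against 0 is significant by Pearson and not by Fisher.

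**How often each outcome would occur.** The documents give no rate of attributed events, so the Group A rates below are assumptions. The probabilities are binomial with n = 20, and the middle column is the remainder.

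| Assumed Group A rate | P(0), no test possible | P(1 to 3), non-significant | P(4 or more), significant |
|---|---|---|---|
| 5% | 35.8% | 63% | 1.6% |
| 10% | 12.2% | 75% | 13.3% |
| 20% | 1.2% | 40% | 58.9% |
| 30% | 0.1% | 11% | 89.3% |

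**What Group A alone can show.** Exact (Clopper-Pearson) 95% intervals are 0 to 16.8% for 0/20, 0.1 to 24.9% for 1/20, 1.2 to 31.7% for 2/20 and 5.7 to 43.7% for 4/20.

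**The case against.** The best defence is that this is one descriptive safety row. No interim analysis, monitoring board or decision rule uses it. A spurious significant result would count against the sponsor's own gel, and the zero in Group B would be printed beside it. All of that stands, and it is why the point is minor. It does not give the p-value any content.

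The zero is also an inference. The plan does not state it, does not say which of the six causality levels count as related, and in Protocol 7.3.6 and SAP 5.3 also groups events by relationship to the trial treatment, a term left undefined for Group B. A non-zero Group B count is possible, but only through misclassification, through counting Unknown as related, or by reading standard care as trial treatment. None of these would measure relatedness to Xonrid.

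A reader might infer three stronger points that the documents do not support:

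- **That administration-site events have the same fault.** SAP 12.3 says only "Tolerability assessment will be based on the evaluation of site administration adverse events" and orders no between-arm test. The term is not defined, and Group B also has irradiated skin, with adjunctive treatment added at G2, so a zero is not established there.
- **That an attribution-free comparison is missing.** Protocol 7.3.6, SAP 5.3 and SAP 11.5 already summarise AEs by system organ class and preferred term regardless of attribution, with chi-square comparisons. A separate row for skin AEs in the irradiated area would be a presentation choice. It would also be incomplete, because Protocol 14.3 keeps signs judged to be lack of efficacy out of the AE record unless they have another cause or are serious.
- **That a false significant finding is likely.** That holds only at assumed attribution rates of about 20% or more. At 5% or 10% the commonest result is a non-significant p-value. Protocol section 4 describes earlier experience with the gel as safe and well tolerated, so the low rates deserve equal weight.

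**Conclusion.** The point holds for study product-related AEs and goes no further. As written, SAP 12.2 sends to chi-square a category in which one arm is expected to be zero, and the p-value is then a function of the Group A count alone. Four patients in 20 read as a significant difference and one to three as none, with no comparative content in either case.

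This rests on three things: relatedness means relatedness to Xonrid, Unknown is not counted as related, and each test has about 20 patients per arm. The threshold of four does not depend on the assumed attribution rates; only the chance of reaching it does. The Group A counts remain useful as description. The comparisons of any, serious and severe AEs and of AE withdrawals are unaffected by this point, as is the primary analysis.

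**What to change.** In SAP 12.2, with matching wording in SAP 5.3 and the table in SAP 11.5:

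- Report product-related AEs for Group A only, for each cancer site, as counts with exact 95% confidence intervals and no between-arm test.
- State which causality categories count as related, including how Unknown is handled.
- Keep the between-arm comparisons for all-cause, serious and severe AEs and for AE withdrawals.
- Record the change in SAP section 13, because Protocol 7.3.6 carries the same comparison and section 13 now lists only the dropped analysis of worst skin toxicity.

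The cost is a few sentences and the loss of two p-values, one per cancer site. No new data are needed.
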